3.3 Safety Population

The safety population is the same as the mITT population for this study.

4 STATISTICAL ANALYSES

4.1 Baseline Characteristics

Demographic and baseline clinical and disease characteristics will be summarized in tables. For continuous variables, the summary will include number, mean, standard deviation, median, minimum, and maximum. Summaries for categorical variables, the number, and percent of subjects in each category will be calculated.

Procedural data will be summarized in tables including information on laboratory analysis, device and techniques, characteristics of the vessel and anticipated treated region, crossing attempts made with standard guidewire and study device, therapeutic treatments employed, device information / accountability.

Vital signs measures and ankle-brachial index will be summarized by study visit. Adverse events on the procedure day and within 30 days after the procedure will be summarized by tabulating the number of percentages of patients experiencing each event. Device and procedure related adverse events will be summarized separately.

Patient data listings including demographic, baseline characteristics, safety data, adverse events, procedural data and endpoints will be provided.

4.2 Efficacy Analyses

Statistical Analysis Plan

Descriptive statistics of the primary efficacy endpoint (total number of CTOs, number and percentage of successful CTO crossings, one-sided 95% CI of the percentage) will be presented. The lower bound of the one-sided 95% CI will be compared to the performance goal of 70.7%.

Summary statistics will be presented for procedural and fluoroscopic time and contrast volume and other secondary endpoints. The summary will include number, mean, standard deviation, median, minimum, maximum, as well as the two-sided 95% CI of the mean and box plots for non-normally distributed data.

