- 1) Lesion success, defined as attainment of <50% final residual stenosis of the target lesion using any percutaneous method.
- 2) Procedure success, defined as device success and the absence of in-hospital MAEs, clinically significant perforation, clinically significant embolization or Grade C or greater dissection not resolved by visual estimate.
- 3) Procedure safety, defined as any in-hospital AE or MAE following use of a therapeutic interventional device.
- 4) Evaluation of total procedural and fluoroscopic time and contrast volume.
- 5) Evaluation of procedure time associated with use of the investigational device.
- 6) Evaluation of utility of ancillary device in addition to investigational device.

Inclusion Criteria:

- 1) Patient is willing and able to provide informed consent.
- 2) Patient is willing and able to comply with the study protocol.
- 3) Patient is > 18 years old.
- 4) Patient has peripheral arterial disease requiring revascularization as evidenced by contrast, CT or MR angiography.
- 5) Patient has at least one but not more than two occluded infrainguinal arteries that are 99-100% stenosed and no flow is observed in the distal lesion except the flow from collateral circulation.
- 6) Target lesion(s) is ≥ 1 cm and ≤ 30 cm in length by visual estimate.
- 7) Target vessel is ≥ 2.0 mm in diameter.
- 8) Patient has Rutherford Classification of 2-5.
- 9) Lesion cannot be crossed by concurrent conventional guidewire.
- 10) Reconstitution of vessel at least 2cm above bifurcation/trifurcation.
- 11) Occlusion can be within previously implanted stent.

Exclusion Criteria:

- 1) Patient has a known sensitivity or allergy to contrast materials that cannot be adequately pre-treated.
- 2) Patient has a known sensitivity or allergy to all anti-platelet medications.
- 3) Patient is pregnant or lactating.
- 4) Patient has a co-existing disease or medical condition contraindicating percutaneous intervention.
- 5) Target lesion is in a bypass graft.

- 6) Patient has had a failed crossing attempt without an intervening intervention on the target limb within the past 14 days.
- 7) Patient has a planned surgical or interventional procedure within 30 days after the study procedure.

**Data Analysis
Center:**

Syntactx
[name]
[name]
[name]

Sponsor:

ReFlow Medical, Inc.
[name]
[name]

**Principal
Investigator:**

[name]

**Angiographic Core
Lab**

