1.3 Subject Population

Subjects with symptomatic peripheral arterial disease (PAD) requiring revascularization. A maximum of 85 subjects > 18 years of age, meeting all the following inclusion and none of the exclusion criteria, and who are willing to sign informed consent will be enrolled.

Patients must meet all the following inclusion criteria to be eligible for enrollment in this trial:

- 1) Patient is willing and able to provide informed consent.
- 2) Patient is willing and able to comply with the study protocol.
- 3) Patient is > 18 years old.
- 4) Patient has peripheral arterial disease requiring revascularization as evidenced by contrast, CT or MR angiography.

Statistical Analysis Plan

- 5) A maximum of 2 lesions can be treated per patient, as identified by the investigator, that have occluded infrainguinal arteries that are 99-100% stenosed and no flow is observed in the distal lesion except the flow from collateral circulation.
- 6) Target lesion is ≥ 1 cm and ≤ 30 cm in length by visual estimate.
- 7) Target vessel is ≥ 2.0 mm in diameter.
- 8) Patient has Rutherford Classification of 2-5.
- 9) Lesion cannot be crossed by concurrent conventional guidewire.
- 10) Reconstitution of vessel at least 2cm above bifurcation/trifurcation.
- 11) Occlusion can be within previously implanted stent.

Patients will be excluded from this trial if any of the following criteria are met:

- 1) Patient has a known sensitivity or allergy to contrast materials that cannot be adequately pre-treated.
- 2) Patient has a known sensitivity or allergy to all anti-platelet medications.
- 3) Patient is pregnant or lactating.
- 4) Patient has a co-existing disease or medical condition contraindicating percutaneous intervention.
- 5) Target lesion is in a bypass graft.
- 6) Patient has had a failed crossing attempt without an intervening intervention on the target limb within the past 14 days.
- 7) Patient has a planned surgical or interventional procedure within 30 days after the study procedure.

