2.2 Secondary Efficacy Endpoints

Statistical Analysis Plan

- Lesion success, defined as attainment of <50% final residual stenosis of the target lesion using any percutaneous method.
- Procedure success, defined as device success and the absence of in-hospital MAEs, clinically significant perforation, clinically significant embolization or Grade C or greater dissection not resolved by visual estimate.
- Evaluation of total procedural and fluoroscopic time and contrast volume.
- Evaluation of procedure time associated with use of the investigational device.
- Evaluation of utility of ancillary device in addition to investigational device.

The angiographic elements of secondary efficacy endpoints will be assessed by an independent core laboratory and the MAE elements adjudicated by an independent CEC. In the event angiographic films are unavailable for assessment by the core lab, site-reported visual assessment will be used for analysis.

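### The 70.7% efficacy test counts CTOs, but the plan does not settle whether a patient contributes one or two, and gives no interval method or rule for two CTOs in one patient

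*SAP*

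**What the plan says.** **The test.** SAP 4.2 plans: "Descriptive statistics of the primary efficacy endpoint (total number of CTOs, number and percentage of successful CTO crossings, one-sided 95% CI of the percentage". It continues: "The lower bound of the one-sided 95% CI will be compared to the performance goal of 70.7" (per cent). Numerator and denominator are therefore both CTOs. The section does not say how the interval is calculated.

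**The sample size.** SAP 1.4 uses an exact binomial calculation with a one-sided error of 0.05, a null rate of 70.7% and an assumed rate of 83.2%. It arrives at 80 subjects, raised to 85 for losses. SAP 3.1 defines the primary (mITT) population by subject.

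**How many CTOs per patient.**
- Pointing to one: the Design entry in the protocol summary and SAP 1.1 each describe the study as crossing one infrainguinal CTO.
- Pointing to two: SAP 1.3, inclusion criterion 5, says "A maximum of 2 lesions can be treated per patient, as identified by the investigator".
- Permitting two without saying that both count in the endpoint: protocol inclusion criterion 5, "Patient has at least one but not more than two occluded infrainguinal arteries", and criterion 6, "Target lesion(s) is ≥ 1 cm and ≤ 30 cm in length by visual estimate".
- Singular wording in SAP 1.3, criterion 6 ("Target lesion is ≥ 1 cm and ≤ 30 cm in length by visual estimate") and SAP 2.2 ("attainment of <50% final residual stenosis of the target lesion using any percutaneous method") fits one CTO, but is also ordinary per-lesion phrasing.

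**Subject-level rate.** SAP 4.3 plans the proportion of subjects with device success and a two-sided 95% CI. It is not compared with 70.7%, and no rule is given for a subject with two CTOs.

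**The concern.** A binomial limit assumes independent observations. Two occlusions in one patient share the patient, the operator and the session, so their outcomes may be positively correlated. If so, the pooled CTO count carries less information than its size suggests. A limit that ignores this sits too close to the observed rate, and the one-sided 5% error of the primary efficacy test can be exceeded.

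The choice of interval matters as well. At this sample size two common methods can disagree at the threshold, and 4.2 names neither. If both points stay open, they will be settled once the crossing results are known.

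**Working it through.** **Inputs.** From SAP 1.4: null rate 0.707 (83.2% minus 12.5 points), assumed rate 0.832, one-sided error 0.05, 80 subjects (85 enrolled). Not in the documents, and assumed here: the number n2 of patients with two counted CTOs, the within-patient correlation rho, and an exact (Clopper-Pearson) limit on pooled CTOs.

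**1. The plan's own efficacy figure.** With one CTO per subject and an exact limit:
- 80 subjects: 64/80 passes (63/80 does not). Error P(X ≥ 64 | 0.707) = 4.05%; power P(X ≥ 64 | 0.832) = 82.2%.
- 85 subjects: 68/85 passes. Error 3.5%, power 82.6%.

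The stated efficacy power of at least 80% therefore reproduces with one observation per subject.

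**2. Interval method alone, no clustering.** The Wald limit at 63/80 is 0.7875 − 1.645 × √(0.7875 × 0.2125 / 80) = 0.7875 − 0.0752 = 0.712. This exceeds 0.707, so 63/80 passes. Error is P(X ≥ 63 | 0.707) = 6.9%, against 4.05% for the exact limit.

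**3. Clustering.** For N subjects, n2 of them with two CTOs, and q = 1 − p:
- P(both crossed) = p² + rho·p·q
- P(neither crossed) = q² + rho·p·q
- Design effect = 1 + rho × 2·n2 / (N + n2)

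The distribution of the total number crossed was convolved exactly. Single counts jump because the test is discrete, so every whole n2 in each band was evaluated. Type I error at a true rate of 70.7%, mean (range):

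| Subjects | Two-CTO share | rho 0 | rho 0.2 | rho 0.5 |
|---|---|---|---|---|
| 80 | 10-20% | 3.9% (3.1-4.6) | 4.2% (3.4-5.1) | 4.8% (3.8-5.9) |
| 80 | 30-50% | 4.1% (3.1-5.0) | 4.9% (3.7-5.9) | 6.2% (4.7-7.5) |
| 80 | 50-100% | 4.1% (3.3-5.0) | 5.4% (4.3-6.6) | 7.3% (5.8-9.0) |
| 85 | 10-20% | 3.7% (3.1-4.6) | 4.1% (3.3-5.0) | 4.7% (3.7-5.7) |
| 85 | 30-50% | 4.1% (3.4-4.9) | 5.0% (4.2-5.8) | 6.3% (5.2-7.3) |
| 85 | 50-100% | 4.1% (3.3-5.0) | 5.4% (4.3-6.5) | 7.3% (5.7-8.7) |

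At rho 0 no count exceeds 5%.

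**4. When the conclusion changes.** Take 40 of 80 patients with two CTOs and rho 0.5. There are 80 + 40 = 120 CTOs, the design effect is 1 + 0.5 × 80/120 = 1.333, and the effective number is 120/1.333 = 90.
- 94/120 (78.3%): unadjusted limit 71.2%, pass; adjusted limit 70.0% (69.97%), fail.
- 95/120: limits 72.1% and 70.9%, pass both ways.

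Over every n2 up to a 50% share, for 80 and 85 subjects at rho 0.5, at most two counts pass unadjusted but fail adjusted. The chance of landing on one is at most 4.1% at a true rate of 70.7%, 16.1% at 78% and 8.9% at 83.2%.

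**5. Does an adjusted limit work?** It was simulated with 400,000 replicates per setting, for 80 and 85 subjects, shares of 10% to 100% and rho 0, 0.2 and 0.5, with rho estimated from the two-CTO pairs and floored at 0:

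| Lower limit | Type I error | Power at 83.2% |
|---|---|---|
| Clopper-Pearson on effective sample size | 3.1-4.5% | 82-98% |
| Robust, logit scale | 4.2-5.0% | 83-99% |
| Robust, plain Wald | 5.9-7.1% | not needed |

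**The case against.** The best defence is that 4.2 does state its unit. It is the CTO, and criterion 5 in SAP 1.3 agrees with it. That stands: a reader might infer that the unit of the 70.7% test is undefined, but it is not. What is open is how many CTOs a patient contributes and how the limit treats two from one patient.

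The effect is also modest where two-CTO patients are few. At a 10-20% share the mean error stays below 5% even at rho 0.5, because the exact limit is conservative to begin with. That stands too. The 7-9% figures need at least half the patients to have two CTOs together with rho 0.5, and the documents support neither value.

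Third, SAP 1.4 makes an exact limit the natural reading. This is plausible, but 1.4 applies the exact binomial only to the sample size, and an exact limit does not correct for clustering. The protocol is available only as a summary, so the full text may say more. The conflict over one or two CTOs nevertheless lies within the SAP itself, between 1.1 and 1.3.

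Finally, a reader might infer that success could be redefined per subject, as both CTOs or either CTO crossed, and tested against 70.7%. The documents plan no such test; the subject-level rate in 4.3 is descriptive.

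**Conclusion.** The point holds and should be fixed. The primary efficacy comparison counts CTOs, the documents disagree on one or up to two per patient, and the visible text gives neither an interval method nor a rule for two CTOs in one patient.

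The size depends on assumed values. With an exact limit, 80 subjects and rho 0.5, mean type I error is 4.8%, 6.2% and 7.3% at two-CTO shares of 10-20%, 30-50% and 50-100%. It is not inflated at rho 0, and clustering does not arise with one CTO per patient. The unnamed interval method is a separate matter: Wald alone gives 6.9%.

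Three stronger readings are not supported. The documents do not establish a two-CTO design; they contradict themselves. They do not show that this trial's error exceeds 5%, because neither the share nor rho is given. Nor is the efficacy sample size wrong: it reproduces with one CTO per subject. Confidence is high for the gap in the text and conditional for its consequence.

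**What to change.** 1. Reconcile the one-CTO statements (protocol Design entry, SAP 1.1) with the two-lesion text (protocol inclusion criterion 5, SAP 1.3 criterion 5), and state in 4.2 how many CTOs per patient enter the test.
2. **If one counts:** say so, designate it before any Wingman attempt, and name the one-sided 95% Clopper-Pearson limit. The timing matters because eligibility itself depends on a guidewire attempt ("Lesion cannot be crossed by concurrent conventional guidewire"), so the designation has to come before the study device's result can influence it. The pass marks are 64/80 or 68/85.
3. **If two can count:** keep the per-CTO rate and compare with 70.7% a one-sided 95% lower limit adjusted for clustering by subject. This can be Clopper-Pearson on the number of CTOs divided by the estimated design effect, or a robust limit on the logit scale. Do not use a plain Wald limit. Add a sensitivity analysis on one pre-designated CTO per subject.
4. State in 4.3 how a subject with two CTOs is classified for the descriptive device success rate.

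The cost is a few sentences, minor programming and, if two CTOs count, a slightly lower limit. Power at a true rate of 83.2% stays above the planned 80%: 82.2% or 82.6% with one CTO per subject, and at least 82% in the simulated two-CTO settings.

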4.3 Safety Analyses

Number and percentage of in-hospital and 30-day major adverse event and the one-sided 95% CI will be presented. The upper bound of the one-sided 95% CI will be compared to the performance goal of 13.0%.

Number and percentage of subjects having 30-day MAEs, device successes, lesion successes, procedure successes and subjects having clinically significant perforation, and the corresponding two-sided 95% CIs will be presented.

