1.1 Design, Treatments and Visits

This is a prospective, multi-center, non-randomized single arm study of the Wingman Catheter to cross a single infrainguinal peripheral chronic total occlusion. This study will be conducted at up to twelve (12) investigational sites in North America and three (3) centers in Europe. Safety and efficacy will be evaluated during the index procedure through 30-day follow-up. The primary endpoint of this study is to assess crossing success with the Wingman device identified as confirmation of guidewire placement in the distal true lumen. The primary safety endpoint of this study will evaluate in-hospital and 30-day MAEs and clinically significant perforations. Secondary endpoints include the lesion (<50% final residual stenosis and grade 'C' or greater dissections created during the procedure that is not resolved by visual estimate) procedural success and safety rates; and the evaluation of procedural and fluoroscopic time/contrast volume. Patient follow-up will be recorded through 30 days post procedure.

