1.4 Sample Size Considerations

The exact binomial distribution is used for calculation of the sample size. The hypotheses and sample size calculations provided in the clinical study protocol are as follows.

The null and alternative hypotheses of the primary efficacy endpoint are:

$$H_0: \pi_{\text{Wingman_efficacy}} \leq \pi_{\text{PG_efficacy}} - \delta_{\text{efficacy}}$$

$$H_A: \pi_{\text{Wingman_efficacy}} > \pi_{\text{PG_efficacy}} - \delta_{\text{efficacy}}$$

where,

$$\pi_{\text{PG_efficacy}} = \text{PG success rate}$$

$$\pi_{\text{Wingman_efficacy}} = \text{Wingman device success rate}$$

Literature Review¹⁻¹¹ indicates that the average success rate of several CTO catheter device types is 83.2%. Using this rate as the historical control and using a non-inferiority margin (δ_{efficacy}) of 12.5% the hypotheses of the primary efficacy endpoint can be rewritten as:

$$H_0: \pi_{\text{Wingman_efficacy}} \leq 70.7\%$$

$$H_A: \pi_{\text{Wingman_efficacy}} > 70.7\%$$

The null and alternative hypotheses of the safety endpoint are:

$$H_0: \pi_{\text{Wingman_safety}} \geq \pi_{\text{PG_safety}} + \delta_{\text{safety}}$$

Statistical Analysis Plan

$$H_A: \pi_{\text{Wingman_safety}} < \pi_{\text{PG_safety}} + \delta_{\text{safety}}$$

where,

$$\pi_{\text{PG_safety}} = \text{PG major adverse event rate}$$

$$\pi_{\text{Wingman_safety}} = \text{Wingman device major adverse event rate}$$

Literature Review¹⁻¹¹ indicates that the average rate of major adverse events, perforations, grade C or higher dissections and embolizations is 5.0%. Using this rate as the historical control, and using a delta of non-inferiority margin (δ_{safety}) 8% for the safety endpoints, the hypotheses can be rewritten as:

$$H_0: \pi_{\text{Wingman_safety}} \geq 13.0\%$$

$$H_A: \pi_{\text{Wingman_safety}} < 13.0\%$$

Assume that the Wingman device has the same success rate and the major adverse event rate as the historical control and further assume that the one-sided type I error rates for the efficacy and safety endpoints are both 0.05. An effective sample size of 80 subjects is needed achieve a power of at least 80% for the efficacy and safety endpoints. To account for a loss of follow up rate of approximately 5%, total enrollment of 85 subjects is required.

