2 ENDPOINT DEFINITIONS

2.1 Primary Efficacy Endpoint

Successful CTO Crossing – While using the Wingman device, successful CTO crossing is identified by successful guidewire placement in the distal true lumen confirmed by angiography with no clinically significant perforations.

All of the angiographic films obtained from this study will be reviewed by an independent core lab. Information from their angiographic review will be recorded on CRFs and tabulated for endpoint analysis. Angiographic review will include assessments of: lesions lengths, occlusion lengths, reference vessel diameter, calcification severity, successful CTO crossing, perforation and dissection.

In the event angiographic films are unavailable for assessment by the core lab, site-reported visual assessments will be used for analysis.

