2.4 Safety Endpoints

Primary Safety – No evidence of significant in-hospital or 30-day MAEs. No evidence of clinically significant perforation¹, clinically significant embolization or ≥Grade C dissection¹ after Wingman CTO crossing after Wingman CTO crossing and prior to adjunctive interventions, confirmed by angiography.

The components of the composite primary safety endpoint include:

- Major Adverse Events (MAEs) defined as death, unplanned target limb major amputation, and emergent target vessel revascularization.
- Clinically significant perforation defined as all perforations requiring intervention (e.g., covered stent, bypass or other surgery).
- Clinically significant embolization defined as those events that result in distal ischemia (e.g., occlusion of run-off vessel resulting in pain or foot discoloration) and/or requires rescue intervention.
- Grade C Dissection or greater with a minimum of a dissection protruding outside the lumen of the vessel persisting after passage of the contrast material.

The components of the primary safety endpoints will be adjudicated by an independent CEC with angiographic elements assessed by an independent core laboratory.

¹ That occur from study device, as adjudicated by the CEC. This would not include perforations or grade C dissections that occur before the use of the study device or those that occur after use of a commercially available therapeutic device (e.g. from atherectomy)

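### Section 4.3 of the SAP, read with its own definition of MAE, tests MAEs alone against a 13.0% goal that was derived for the four-part safety composite

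*SAP*

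**What the plan says.** Four places in the SAP bear on what the primary safety test counts.

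- **Section 2.4 (Safety Endpoints)** makes primary safety a composite of four components: MAE, clinically significant perforation, clinically significant embolization, and dissection of Grade C or worse. MAE is one of the four and is narrow: "Major Adverse Events (MAEs) defined as death, unplanned target limb major amputation, and emergent target vessel revascularization". The protocol summary gives the same structure.
- **Section 1.4 (Sample Size Considerations)** says that the literature "indicates that the average rate of major adverse events, perforations, grade C or higher dissections and embolizations is 5.0" percent, adds a margin of 8%, and so arrives at 13.0%. It nevertheless labels the tested parameter the major adverse event rate: "Assume that the Wingman device has the same success rate and the major adverse event rate as the historical control".
- **Section 4.3 (Safety Analyses)** states the analysis: "Number and percentage of in-hospital and 30-day major adverse event and the one-sided 95% CI will be presented". It continues: "The upper bound of the one-sided 95% CI will be compared to the performance goal of 13.0" percent. Its next paragraph lists, with two-sided intervals, "Number and percentage of subjects having 30-day MAEs, device successes, lesion successes, procedure successes and subjects having clinically significant perforation".
- **Section 1.1 (Design, Treatments and Visits)** describes the endpoint in a third way: "The primary safety endpoint of this study will evaluate in-hospital and 30-day MAEs and clinically significant perforations".

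Elsewhere (Sections 3.1, 4.4 and 4.6) the SAP refers to the primary endpoints only in general terms, for the analysis population, poolability and the tipping-point analysis. Nothing in Section 4 names the composite or says that its rate is compared with 13.0%.

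**The concern.** A performance goal has meaning only for the quantity it was derived for. The 13.0% allows for four kinds of event. If only MAEs are counted against it, the allowance for perforation, embolization and dissection becomes extra room for MAEs, and those other harms are not limited at all.

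On that literal reading, an embolization or Grade C dissection that does not lead to an MAE enters no primary test. A perforation that does not lead to an MAE enters only the efficacy test, because Section 2.1 requires "successful guidewire placement in the distal true lumen confirmed by angiography with no clinically significant perforations". These are the events most directly attributable to a crossing device. The one-sided 5% error rate would then not apply to the endpoint defined in Section 2.4. Two analysts following the same SAP could reach opposite conclusions on primary safety.

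**Working it through.** **Inputs.** From Section 1.4: historical rate 5.0%, margin 8%, one-sided alpha 0.05, effective sample size 80, enrollment 85, exact binomial for the sample size. Section 4.3 names no interval method, so I assume the exact (Clopper-Pearson) one-sided limit. The documents give no rate for MAE alone, so I use a range of assumed values.

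**1. The plan's own figures.** 5.0% + 8% = 13.0%, as stated. Enrollment: 80 / (1 − 0.05) = 84.2, rounded up to 85, as stated. With 80 subjects the exact test rejects at 5 or fewer events. Its power at a true rate of 5% is P(X ≤ 5 | 80, 0.05) = 78.9%, marginally below the stated minimum of 80%. That is a separate point and does not affect this one.

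**2. Pass rule.** The test passes when x events satisfy P(X ≤ x | n, 0.13) ≤ 0.05. The largest such x is 5 at both sample sizes. The upper limit is the 95th percentile of Beta(x + 1, n − x).

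| Events | Upper limit, n = 80 | Upper limit, n = 85 | Against 13.0% |
|---|---|---|---|
| 2 | 7.7% | 7.2% | pass |
| 5 | 12.7% | 12.0% | pass |
| 6 | 14.3% | 13.5% | fail |

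**3. Composite test at the null.** At a true composite rate of 13%, P(X ≤ 5) = 4.3% for n = 80 and 2.8% for n = 85. The type I error is controlled.

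**4. MAE-only test.** The same rule applies to MAEs alone, so the chance of passing, P(X ≤ 5 | n, MAE rate), depends only on the MAE rate.

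| Assumed MAE rate | Passes, n = 80 | Passes, n = 85 |
|---|---|---|
| 1% | 99.98% | 99.98% |
| 2% | 99.5% | 99.3% |
| 3% | 96.7% | 95.7% |
| 5% | 78.9% | 74.8% |
| 8% | 37.5% | 31.7% |

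These figures hold even if the composite rate is 13% or more. The MAE-only test passes at least 95% of the time when the MAE rate is no higher than about 3.3% (n = 80) or 3.1% (n = 85).

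**5. When the conclusions differ.** The two readings disagree whenever at most 5 subjects have an MAE but at least 6 have some component. For example, 2 subjects have an MAE and 4 others have embolization or Grade C dissection, with no perforation.

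- Composite: 6/85 = 7.1%, upper limit 13.5%, fail. For 6/80 the limit is 14.3%, fail.
- MAE only: 2/85 = 2.4%, upper limit 7.2%, pass. For 2/80 the limit is 7.7%, pass.

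**The case against.** The best defence is that the SAP uses the label loosely and means the composite. Section 1.4 attaches the words 'major adverse event rate' to the four-part rate. Section 4.3 uses similar words with the same 13.0%, and the SAP has only one safety goal and one primary safety endpoint. Section 4.3 also lists 30-day MAEs again in its second paragraph, which would be largely redundant if the first paragraph already counted MAEs only. This reading is tenable and may well be what the sponsor intends.

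It does not settle the text. It needs Section 4.3 to use a term in a sense other than the one Section 2.4 gives it. The repeated listing is also consistent with in-hospital plus 30-day MAEs in the first paragraph and 30-day MAEs alone in the second. Section 1.1 offers yet another version.

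Some narrower objections stand:

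- A perforation needing intervention could also qualify as an emergent target vessel revascularization and so count as an MAE.
- Embolization and unresolved dissection enter procedure success, which Section 4.3 reports, and Section 4.1 tabulates adverse events. These harms would be reported, but not tested.
- The MAE rates in the table are assumptions.
- The full protocol and the mock tables were not available and might resolve the matter.

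None of these makes the SAP say that the composite is tested.

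**Conclusion.** The concern holds. By its own defined term, Section 4.3 compares one component of primary safety with the goal for all four, and no analysis sentence corrects this. What is established is a conflict in the text of a primary hypothesis test, not that the sponsor will in fact count MAEs alone.

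The size depends on the unknown MAE rate. If that rate is about 3% or lower, the literal test passes at least 95.7% of the time at either sample size, while the composite test passes 4.3% (n = 80) or 2.8% (n = 85) of the time at a composite rate of 13%. At MAE rates of 5% or 8% the literal test is less lenient, but it still places no limit on the other three components. All figures assume an exact limit. The numerator of a primary test should not be left to inference, so this must be fixed.

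**What to change.** Replace the first paragraph of Section 4.3 with text such as:

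> The number and percentage of subjects with one or more components of the Section 2.4 primary safety composite (in-hospital or 30-day MAE, clinically significant perforation, clinically significant embolization, Grade C or greater dissection) will be presented. The exact (Clopper-Pearson) one-sided 95% upper limit will be compared with 13.0%.

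In Section 1.4, relabel the safety parameter as the composite event rate. Bring Section 1.1 into line with Section 2.4. Report MAE, perforation, embolization and dissection separately as descriptive results, each with a two-sided 95% interval.

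Naming the interval method is a secondary gain. A Wald limit would let 6 events pass (12.3% for 6/80, 11.6% for 6/85), with a type I error of 9.1% or 6.3%.

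The cost is SAP wording only, because Section 2.4 already has every component adjudicated by the CEC, with angiographic elements read by the core laboratory. The observed primary safety rate may look less favourable. The protocol summary planned last follow-up for Q1 2019 and the SAP is dated 20 May 2019, so the change should be dated and should state whether safety results had been seen.
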